7.1.11 Hy's Law

Cases where a subject shows elevations in liver biochemistry may require further evaluation and occurrences of AST or ALT $\geq 3 \times$ ULN together with total bilirubin $\geq 2 \times$ ULN may need to be reported as SAEs. Please refer to Appendix C for further instruction on cases of increases in liver biochemistry and evaluation of Hy's law.

7.2 Recording and Grading of Adverse Events

7.2.1 Recording

All observed or volunteered adverse events, regardless of treatment group, severity, suspected causal relationship, expectedness, or seriousness will be recorded.

A clinically significant change in a physical examination finding or an abnormal test result should be recorded as an AE, if it:

- is associated with accompanying symptoms
- requires additional diagnostic testing or medical or surgical intervention
- leads to a change in study dosing or discontinuation from the study
- requires additional concomitant drug treatment or other therapy, or
- is considered clinically significant by the investigator or sponsor

An abnormal test result that is subsequently determined to be in error does not require recording as an adverse event, even if it originally met one or more of the above criteria.

7.2.2 Grading severity

All adverse events will be graded based on the NCI CTCAE version 5.0. A copy of the CTCAE Version 5.0 can be downloaded from the CTEP home page (<http://ctep.cancer.gov>). All appropriate treatment areas should have access to a copy of the CTCAE Version 5.0.

7.2.3 Attributing causality

After assigning a grade to an adverse event, the investigator must evaluate all AEs for possible causal relationship to the investigational agent(s). Causality attribution will be decided using the criteria outlined in *Table 1*.

Table 1. Relationship of Adverse Event to Study Drug

Relationship	Description
Unrelated	AE is clearly not related
Unlikely	AE is doubtfully related
Possible	AE may be related
Probable	AE is likely related
Definite	AE is clearly related

7.3 Reporting Serious Adverse Events

7.3.1 Reporting serious adverse events

All SAEs, events determined to be medically significant by the treating Investigator, and unknown reactions or unexpected events should be reported to the PCCTC within 24 hours of knowledge of the event using the contact information below. The initial report should include the following information at a minimum:

- protocol # and title

- subject identification number, sex, age at event
- date the event occurred
- description of the SAE
- causal relationship to the study treatment(s)

The SAE Report Form will be used for reporting each SAE and should be submitted to the PCCTC Project Coordinator within 24 hours. The PCCTC will facilitate all SAE report form submissions to lead site/sponsor.

Grade, relationship, action taken, concomitant medications, outcome, etc. should be reported to the PCCTC as soon as possible.

Follow-up of adverse events should continue until the event and any sequela resolve or stabilize at a level acceptable to the investigator.

SAE contact information for the PCCTC is listed below.

PCCTC:
Prostate Cancer Clinical Trials Consortium
Email: [contact]

The PCCTC will be responsible for reporting to AstraZeneca by facsimile any Serious Adverse Event that occurs during the SAE reporting period. The PCCTC will report the SAE within 24 hours of PCCTC first awareness of the event (immediately if the event is fatal or life-threatening).

The PCCTC will disseminate information regarding SAEs to the participating sites provided by AstraZeneca within five (5) days of review of the information by the Sponsor Principal Investigator (or her designee in the event of extended absence) only in the case that the event(s) is believed to be related (i.e., possibly, probably, or definitely) to the study medication.

The PCCTC will be responsible for reporting of events to the FDA and supporters, as appropriate (outlined below).

7.3.1 Serious Adverse Event Reporting to the FDA and AstraZeneca

It is the responsibility of MSKCC to submit an investigational new drug application (IND) or receive an IND exemption from the FDA for clinical trials conducted with investigational agents and to ensure that FDA and all participating investigators are promptly informed of significant new AEs or risks with respect to the investigational agent.

Serious, unexpected AEs believed to be definitely, probably, or possibly related to the study treatment will be reported to the FDA by MSKCC in accordance with IND regulations. AEs that must be reported to the FDA will also be concurrently submitted to AstraZeneca by the PCCTC. *A cover page should accompany the SAE form indicating the following:

- Investigator Sponsored Study (ISS)

- The investigator IND number assigned by the FDA, if applicable
- The investigator's name and address
- The trial name/title and AstraZeneca ISS reference number

* Investigative site must also indicate, either in the SAE report or the cover page, the causality of events in relation to all study medications and if the SAE is related to disease progression, as determined by the principal investigator.

* Send SAE report and accompanying cover page by way of email to [contact]

If a non-serious AE believed to be definitely, probably or possibly related to olaparib or durvalumab becomes serious, this and other relevant follow-up information must also be provided to AstraZeneca and the FDA if applicable.

SAEs that do not require expedited reporting to the FDA need to be reported to AstraZeneca preferably using the MedDRA coding language for SAEs. This information should be reported on a monthly basis and under no circumstance less frequently than quarterly.

All SAEs have to be reported to AstraZeneca by the PCCTC, whether or not considered causally related to the investigational product. All SAEs will be documented. The investigator is responsible for informing the IRB and/or the Regulatory Authority of the SAE as per local requirements.

An SAE which occurs after consent and before a subject starts study treatment does not need to be reported if it is unrelated to screening procedures. All SAEs that occur once a subject has started study treatment will be reported irrespective of causality. Non-serious AEs will be collected from the time consent is given, throughout the treatment period and up to and including the 30 days after the last dose of study drug, unless the toxicity is considered related to study drug. If related to study drug, non-serious AEs and SAEs will be collected from the time the consent is given, throughout the treatment period and up to and including the 90 days after the last dose of study drug. After withdrawal from treatment, subjects must be followed-up for all existing and new AEs for 90 calendar days after the last dose of trial drug and/or until event resolution. All new AEs occurring during that period must be recorded (if SAEs, then they must be reported to the FDA, if applicable, and AstraZeneca). All study-related toxicities/SAEs must be followed until resolution, unless in the Investigator's opinion, the condition is unlikely to resolve due to the subject's underlying disease.

7.3.2 Reporting of paternal exposure

Male subjects should refrain from fathering a child or donating sperm during the study and for 180 days after the last dose of durvalumab or olaparib therapy.

Pregnancy of the subject's partner is not considered to be an AE. However, if allowed per local procedures, the outcome of all pregnancies (spontaneous miscarriage, elective termination, ectopic pregnancy, normal birth, or congenital abnormality) occurring from

the date of the first dose until 180 days after the last dose of durvalumab or olaparib if possible, will be followed up and documented.

7.3.3 Other events that require reporting

Overdose

An overdose is defined as a patient receiving a dose of durvalumab or olaparib in excess of that specified in the IB, unless otherwise specified in this protocol.

Any overdose of a study subject with durvalumab or olaparib, with or without associated AEs/SAEs, is required to be reported within 24 hours of knowledge of the event to PCCTC. PCCTC will report to the sponsor and AstraZeneca/MedImmune Patient Safety or designee. If the overdose results in an AE, the AE must also be recorded as an AE (see Section 7.2). Overdose does not automatically make an AE serious, but if the consequences of the overdose are serious, for example death or hospitalization, the event is serious and must be recorded and reported as an SAE. There is currently no specific treatment in the event of an overdose of durvalumab or olaparib.

The investigator will use clinical judgment to treat any overdose.

New Cancer

The development of a new cancer should be regarded as an SAE. New primary cancers are those that are not the primary reason for the administration of the IP and have been identified after the patient's inclusion in this study.

Hepatic function abnormality

Hepatic function abnormality that fulfills the biochemical criteria of a potential Hy's Law case in a study subject, with or without associated clinical manifestations, is required to be reported as "hepatic function abnormal" within 24 hours of knowledge of the event to the PCCTC, unless a definitive underlying diagnosis for the abnormality (e.g., cholelithiasis or bile duct obstruction) that is unrelated to investigational product has been confirmed. The criteria for a potential Hy's Law case is Aspartate Aminotransferase (AST) or Alanine Aminotransferase (ALT) ≥ 3 times Upper Limit of Normal (ULN) together with Total Bilirubin (TBL) ≥ 2 times ULN at any point during the study following the start of study medication irrespective of an increase in Alkaline Phosphatase (ALP).

- If the definitive underlying diagnosis for the abnormality has been established and is unrelated to investigational product, the decision to continue dosing of the study subject will be based on the clinical judgment of the investigator.
- If no definitive underlying diagnosis for the abnormality is established, dosing of the study subject must be interrupted immediately. Follow-up investigations and inquiries must be initiated by the investigational site without delay.

Each reported event of hepatic function abnormality (meeting criteria for Hy's Law as per above) will be followed by the investigator and evaluated by the sponsor and AstraZeneca/MedImmune.

7.3.3 Reporting of deaths

All deaths that occur during the study, or within the protocol-defined 90-day post-last dose of study drug must be reported to the PCCTC as follows:

- Death that is clearly the result of disease progression should be documented but should not be reported as an SAE.
- Where death is not due (or not clearly due) to progression of the disease under study, the AE causing the death must be reported to AstraZeneca as a SAE within 24 hours. The report should contain a comment regarding the co-involvement of progression of disease, if appropriate, and should assign main and contributory causes of death.
- Deaths with an unknown cause should always be reported as a SAE.

Deaths that occur following the protocol-defined 90-day post-last-dose of durvalumab safety follow-up period will be documented, but will not be reported as an SAE.

The PCCTC will be responsible for reporting deaths to AstraZeneca.

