5.4.1 Durvalumab Dose Modification

Dose reductions for durvalumab are not permitted. For dose modification and toxicity management guidelines for durvalumab, refer to Appendix G.

5.4.2 *Olaparib dose levels*

Dose Level	Olaparib
Level 0	300 mg BID
Level -1	250 mg BID
Level -2	200 mg BID
Level -3	Discontinue

Subjects requiring more than two dose reductions will have to discontinue olaparib. 100 mg and 150 mg tablets will be supplied for olaparib.

5.4.3 *Toxicities that require discontinuation from study treatment*

Protocol therapy should be discontinued if a subject experiences:

- Any CTCAE Grade 4 toxicity with the exception of:
 - CTCAE Grade 4 neutropenia of 5 days or fewer duration
 - CTCAE Grade 4 nausea/vomiting or diarrhea that resolves to Grade 3 or less within 72 hours
 - CTCAE Grade 4 laboratory abnormalities that can be readily corrected with 72 hours and do not result in hospitalization.
- CTCAE Grade 3 thrombocytopenia with hemorrhage
- CTCAE Grade 3 febrile neutropenia
- Hy's Law (AST or ALT >3x ULN with concomitant serum bilirubin >2x ULN and no alternate etiology)
- Bone marrow findings consistent with myelodysplastic syndrome (MDS)/acute myeloid leukemia (AML)

5.5 **Concomitant Medications and Supportive Care**

Because of the potential for drug-drug interaction, the concurrent use of all other drugs, over-the-counter medications, and alternative therapies must be documented on the eCRF.

Subjects should not donate blood while participating in this study or for at least 90 days following the last infusion of durvalumab or olaparib.

Refer to Appendix D for more information on concomitant medications and supportive care guidance.

5.6 **Other Concomitant Treatment**

Any medications, with the exceptions noted in Appendix D, which are considered necessary for the subject's welfare, and which it is believed will not interfere with the study medication, may be given at the discretion of the Investigator, providing the medications, the doses, dates and reasons for administration are recorded in the EDC.

In addition, any diagnostic, therapeutic or surgical procedure performed during the study period must be recorded in the EDC.

All medications (prescriptions or over-the-counter medications) continued at the start of the trial (from the time of informed consent) or started during the study or until 30 days from the end of the last protocol treatment and different from the study medication must be documented.

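### The section on reporting deaths sets two different cut-offs for SAE reporting: 90 days after the last study drug, and 90 days after the last durvalumab alone

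*Combined protocol and SAP*

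**What the plan says.** Two sections are numbered 7.3.3; the one at issue is headed Reporting of deaths. It opens: "All deaths that occur during the study, or within the protocol-defined 90-day post-last dose of study drug must be reported to the PCCTC". The bullets beneath make a death that is not due, or not clearly due, to progression a 24-hour SAE report to AstraZeneca, and add: "Deaths with an unknown cause should always be reported as a SAE". A death clearly caused by progression is documented but is not an SAE. The section then closes its SAE rules with: "Deaths that occur following the protocol-defined 90-day post-last-dose of durvalumab safety follow-up period will be documented, but will not be reported as an SAE".

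Section 7.3.1, Serious Adverse Event Reporting to the FDA and AstraZeneca, does not single out durvalumab. After withdrawal from treatment, "subjects must be followed-up for all existing and new AEs for 90 calendar days after the last dose of trial drug". It also states "All SAEs that occur once a subject has started study treatment will be reported irrespective of causality" and "All SAEs have to be reported to AstraZeneca by the PCCTC, whether or not considered causally related to the investigational product".

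Section 5.4 allows a man who stops one agent for toxicity or a long interruption to continue the other until progression, at the investigator's discretion. Section 6.5 allows the same after discussion with the Sponsor Principal Investigator when toxicity is attributed to one agent.

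**The concern.** The opening and closing of one section set different end points for the same duty. A man who stops durvalumab and stays on olaparib may pass the durvalumab cut-off while still taking an investigational drug. If he then dies of something other than clear progression, the opening text makes the death an SAE and the closing sentence says it is not reported as one.

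A site could reasonably take the closing sentence literally. Elsewhere, post-dose windows meant to cover both agents name both: blood donation is barred "for at least 90 days following the last infusion of durvalumab or olaparib" (Section 5.5), and fathering a child or donating sperm "for 180 days after the last dose of durvalumab or olaparib therapy" (Section 7.3.2). The closing sentence names one.

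What is at stake is the prompt report. The death would still be documented, and a fatal AE would still appear in the Section 10.4.2 summary. But under Section 11.5 the Sponsor Principal Investigator reviews SAEs as they are reported and then judges whether the study can safely continue. A non-progression or unexplained death on olaparib, or in the weeks after it, belongs in that stream.

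**Working it through.** The plan gives no figure to reproduce. The check compares the two windows on a study calendar.

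**Inputs**
- Cycle length 28 days (Appendix B); 24 planned cycles (Section 5.7).
- Durvalumab on Day 1 of each cycle (Section 6.1).
- Olaparib twice daily, continuously for 24 months (Sections 5 and 6.2).
- Both cut-offs are 90 days after a last dose (Section 7.3.3, Reporting of deaths).
- Assumptions: Cycle 1 Day 1 is study day 1, there are no delays, and olaparib runs to the end of Cycle 24.

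**Formulas**
- Last olaparib = 24 × 28 = day 672. Study-drug window ends at 672 + 90 = day 762.
- Last durvalumab at Cycle k = day 28(k − 1) + 1. Durvalumab window ends at day 28(k − 1) + 91.
- Days in conflict = 762 − [28(k − 1) + 91].
- Of these, days on olaparib = 672 − [28(k − 1) + 91], or 0 if negative.

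| Last durvalumab | Durvalumab window ends | Days in conflict | Of which on olaparib |
|---|---|---|---|
| Cycle 24 (completer) | 644 + 91 = day 735 | 762 − 735 = 27 | 0 |
| Cycle 12 (assumed) | 308 + 91 = day 399 | 762 − 399 = 363 | 672 − 399 = 273 |
| Cycle 6 (assumed) | 140 + 91 = day 231 | 762 − 231 = 531 | 672 − 231 = 441 |
| Cycle 1 (assumed) | 0 + 91 = day 91 | 762 − 91 = 671 | 672 − 91 = 581 |

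Only the 27-day gap follows from the planned schedule. The other rows show how far apart the windows can move under Sections 5.4 and 6.5. All are days on which the instructions conflict, not counts of deaths.

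**How many men might this reach?** Section 1.2.7 reports permanent discontinuation of durvalumab for an AE in about 9% of monotherapy subjects. If that rate carried over to this combination and population, which is an assumption, 0.09 × 32 = 2.9, or about 3 men, would stop durvalumab. How many of those would stay on olaparib is not given, so the range is 0 to 3. The documents give no rate of non-progression death, so the count of affected deaths cannot be derived.

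**Which deaths are outside the conflict?** Deaths within 90 days of the last durvalumab dose are treated alike by both sentences. So are deaths clearly due to progression, which neither sentence makes an SAE.

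**The case against.** The best reply is that the closing sentence is loosely worded and not a separate rule. It refers back to a period the protocol has defined, and no durvalumab-only safety period is defined anywhere. The period that does exist is the 90 days after the last trial drug in Section 7.3.1, and a man still on olaparib has not entered it. The protocol's drafting is loose elsewhere too: the blood-donation rule in Section 5.5 speaks of an infusion of olaparib, which is a tablet, so little should be inferred from when it names one drug or two.

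Other rules also catch these deaths. Any event resulting in death is an SAE (Section 7.1.4), and all SAEs go to the PCCTC within 24 hours (Section 7.3.1, Reporting serious adverse events). The PCCTC, not the site, reports deaths to AstraZeneca. MDS/AML, new primary malignancy and pneumonitis are reportable in their own right under Section 7.1.10. The long gaps also depend on olaparib continuing alone, which is discretionary.

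Most of this stands. The charitable reading is plausible and probably what was meant, and the overlapping rules make a lost report less likely. But the sentence still names durvalumab alone, and it is the most specific statement on when deaths stop being SAEs. The surrounding rules show that it conflicts with the rest of Section 7.3; they do not tell a site which instruction prevails.

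**Conclusion.** The concern holds. Section 7.3.3, Reporting of deaths, gives two cut-offs that disagree by 27 days for a man who completes both drugs. They disagree by 363 to 671 days in the illustrated cases where durvalumab is last given between Cycle 12 and Cycle 1 and olaparib runs to day 672. Followed literally, the closing sentence would drop the 24-hour SAE report for a non-progression or unexplained death on or soon after olaparib. The rest of Section 7.3 requires that report, so the defect is a pair of conflicting instructions. The number of deaths affected is unknown and may be zero. The sample size, the primary endpoint and the efficacy analysis are untouched. It should be corrected because it is an operative safety rule and the intended reading is clear from the surrounding text.

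**What to change.** In the closing sentence on SAE reporting in Reporting of deaths, replace the reference to the last dose of durvalumab with: *after the last dose of either study drug (durvalumab or olaparib), whichever is later*. The sentence then agrees with the section's opening and with the 90-day follow-up in Section 7.3.1. A 24-cycle completer then has one window, ending on day 762.

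The cost is one phrase in the next amendment, with no new data, visits or staff. The downside is at most a few additional SAE reports.

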7.4 Safety Reports

- PCCTC will distribute outside safety reports to the participating sites.
- Participating sites must submit safety reports to their institution's IRB/PBs per participating site guidelines.

8. CRITERIA FOR OUTCOME ASSESSMENT/THERAPEUTIC RESPONSE

8.1 Therapeutic Response

8.1.1 PSA

This trial will measure PSA monthly for the first 24 months. The primary endpoint is an undetectable PSA at 24 months with non-castrate levels of testosterone (>150 ng/dL).

9. DATA REPORTING AND REGULATORY REQUIREMENTS

9.1 Data Collection and Management

Data collected during this study will be entered into a secure database.

9.1.1 *Electronic Case Report Forms (eCRFs)*

Standardized eCRFs and CRF Completion Guidelines will be created by the PCCTC for the collection of study data. Access and training for PCCTC Medidata Rave EDC will be made available to participating sites upon local regulatory approval. The participating site investigator is responsible for ensuring eCRFs are completed accurately and in a timely manner.

9.1.2 *Source documents*

Source documentation refers to original records of observations, clinical findings and evaluations that are subsequently recorded as data. Source documentation will be made available to support the subject's research record.

9.1.3 *Record retention*

The investigator will maintain adequate and accurate records to enable the conduct of the study to be fully documented and the study data to be subsequently verified. After study closure, the investigator will maintain all source documents and study-related documents. Records are to be retained and securely stored until the later of: (a) two (2) years following the date a New Drug Application is approved for the Study Drug that is the subject of the Clinical Trial; or (b) two (2) years after the Investigational New Drug Application for such Study Drug is terminated or withdrawn, or such longer period of time as may be required by Participant policies, applicable laws, rules or regulations.

9.2 **Study Monitoring and Quality Assurance**

9.2.1 *Data and Safety Monitoring*

The Data and Safety Monitoring Plans (DSMP) at MSKCC were approved by the National Cancer Institute in September 2001. The plans address the new policies set forth by the NCI in the document entitled Policy of the National Cancer Institute for Data and Safety Monitoring of Clinical Trials. The DSMPs at MSKCC were established and are monitored by the Office of Clinical Research.

There are several different mechanisms by which clinical trials are monitored for data, safety, and quality. There are institutional processes in place for quality assurance (e.g., protocol monitoring, compliance and data verification audits, therapeutic response, and staff education on clinical research quality assurance) and departmental procedures for quality control, plus there are two institutional committees that are responsible for monitoring the activities of our clinical trials programs. There are several committees: Data and Safety Monitoring Committee (DSMC) for Phase I and II clinical trials, and the Data and Safety Monitoring Board (DSMB) for Phase III clinical trials, report to the MSKCC Research Council and Institutional Review Board. As a moderate risk trial, this study will be monitored by DSMC twice per year.

9.2.2 *Data Monitoring, Auditing, and Quality Assurance*

In addition to review by DSMC, PCCTC will conduct regularly scheduled monitoring visits. Reports will be generated by the PCCTC to monitor subject accruals and the completeness of data. Routine data quality reports will be generated to assess missing data and inconsistencies. Accrual rates and the extent and accuracy of evaluations and follow-up will be monitored periodically throughout the study period, and potential problems will be brought to the attention of the Sponsor Principal Investigator for discussion and action.

The monitoring visit will include a review of source documentation to evaluate:

- Regulatory/IRB compliance (review of current protocol and amendments, Informed consent documents and procedures, annual continuing review reports, AEs/SAEs)
- Protocol defined treatment compliance

- Subject records
 - A signed and dated informed consent form for each subject
 - Adherence to eligibility criteria
 - Source Data Verification for identified subjects

Monitoring findings will be reviewed and disseminated to the site investigators and staff.

The PCCTC may also perform site audits. If a site is notified of an external audit relating to this study, the site should notify the PCCTC immediately. The PCCTC and/or Monitors assigned to this study will provide site support during audits (quality control and/or regulatory agency) including review and assisting sites with responses to audit findings.

9.2.3 *Data Review and Queries*

The PCCTC will review data and source documentation. Data will be monitored and source data verified as defined in the Monitoring and Data Management plans and discrepancies will be issued as queries in the EDC. In addition, the PCCTC will review data for logic, consistency, and obvious anomalies.

